## Summary

### Objectives:

#### Research Questions:

1. What is the natural history of COVID-19 related olfactory dysfunction?
2. Is there a therapeutic benefit of omega-3 supplement administration for COVID-19 related olfactory dysfunction?

The aim of the study is to gain an understanding of the natural history of olfactory dysfunction associated with COVID-19 infection in addition to evaluating whether there is a therapeutic role for omega-3 supplementation during the subacute period. Through this study, we hope to provide anticipatory guidance regarding the prognosis for COVID-19 related olfactory dysfunction as well as assess a potential therapeutic intervention.

### Background:

Infection with the novel coronavirus (COVID-19) has been linked to new-onset olfactory dysfunction, often as the only presenting symptom. In one multicenter European study, 85.6% of patients with mild to moderate symptoms reported hyposmia or anosmia with early recovery of olfactory function in just under half of patients. However, the pathogenesis and natural history of COVID-19 related olfactory dysfunction is poorly understood.

Anosmia most commonly arises in association with sinonasal disease or post-infectious or post-traumatic disorders. Notably, olfactory loss has been associated with impaired quality of life, higher rates of depression, and even increased mortality risk. Spontaneous recovery has been observed in patients with post-infectious olfactory dysfunction, typically over a period of months to years, with an estimated one-third of patients demonstrating meaningful improvement after one year.

Smell retraining therapy appears to be an effective therapeutic option for patients with post-infectious olfactory dysfunction, particularly for patients who initiate treatment within one year from onset of symptoms, but requires an intervention period of at least three to four months. Various pharmacotherapies have been investigated in the treatment of post-infectious anosmia but none have clearly demonstrated utility with the exception of a possible benefit for nasal steroid irrigations in combination with smell retraining therapy.

More recently, omega-3 polyunsaturated fat supplementation has emerged as a promising pharmacotherapy for olfactory dysfunction in patients without sinonasal disease. Omega-3 fatty acid deficient mice demonstrate evidence of olfactory dysfunction and mice receiving omega-3

### Primary and Secondary Study Endpoints:

The primary endpoint of this study is a Brief Smell Identification Test, a standardized and validated objective measure of olfactory function, administered 6 weeks from symptom onset.

The secondary endpoints of this study include patient-reported outcome measure surveys, a modified Brief Questionnaire of Olfactory Dysfunction - Negative Statements (QOD-NS) survey and Sino-Nasal Outcome Test (SNOT-22), administered at time points of 1, 2, 4, and 6 weeks after symptom onset.

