### **Settings and Resources**

#### Specify Other Setting of Human Research

This study will be executed at the Icahn School of Medicine at Mount Sinai. Patients will be recruited from the practices of faculty in the Department of Otolaryngology – Head and Neck Surgery and via the STOP COVID NYC web-based application (IRB 20-03271). All research will be conducted at the Icahn School of Medicine at Mount Sinai. No research will be conducted outside of the Icahn School of Medicine at Mount Sinai.

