### **Subjects**

#### Inclusion Criteria

Adults ( $\geq 18$  years of age) with self-reported new-onset olfactory dysfunction and a positive COVID-19 diagnosis will be deemed eligible for inclusion.

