#### Exclusion Criteria

- Patients  $< 18$  years of age
- Patients who are unable to provide informed consent
- Patients without a positive COVID-19 PCR result obtained through nasopharyngeal swab
- Patients with a COVID-19 diagnosis but without self-reported anosmia
- Patients with severe COVID-19 disease as defined by the Mount Sinai Health System Treatment Guidelines for SARS-COV-2 (requiring high flow nasal cannula, non-rebreather, CPAP/BIPAP, or mechanical ventilation OR patients requiring pressor medication OR patients with evidence of end organ damage)
- Patients with pre-existing self-reported olfactory dysfunction
- Patients with a history of chronic nasal/sinus infections (rhinosinusitis) or history of endoscopic sinus surgery
- Patients using nasal steroid sprays or irrigations for any reason
- Patients who are prisoners of the state
- Patients who have psychiatric or developmental disorder conditions that may impair ability to provide informed consent

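### The natural-history question is timed from symptom onset but patients enter at a later, unlimited time, so an onset-based prognosis would be too pessimistic to the extent that early recoverers under-enrol

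*Protocol*

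**What the plan says.** Under Research Questions in the Protocol, the first question is "What is the natural history of COVID-19 related olfactory dysfunction", and the stated purpose is that "we hope to provide anticipatory guidance regarding the prognosis for COVID-19 related olfactory dysfunction".

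Primary and Secondary Study Endpoints places the Brief Smell Identification Test (BSIT) on an onset clock, "administered 6 weeks from symptom onset". The two surveys (QOD-NS and SNOT-22) are "administered at time points of 1, 2, 4, and 6 weeks after symptom onset". Description of Procedures Being Performed repeats both.

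Entry takes several steps:
- Inclusion Criteria asks for "self-reported new-onset olfactory dysfunction and a positive COVID-19 diagnosis".
- Exclusion Criteria removes "Patients without a positive COVID-19 PCR result obtained through nasopharyngeal swab" and those with no self-reported anosmia.
- How Participants Will Be Identified describes, in the present tense, people who have self-reported anosmia.
- How Research Will Be Introduced to Participants has the team make contact after identification.
- The Consent sections add sending the form, reading time, and a call from the participant to arrange signing.

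No section caps the time from onset to enrolment.

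On sources, Specify Other Setting of Human Research says "Patients will be recruited from the practices of faculty in the Department of Otolaryngology" and names a web application. Specify Other Recruitment Method adds a data-warehouse list of COVID-positive patients.

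The two sections that describe data collection list follow-up at one, two, four and six weeks without naming onset as the origin. One of them puts an initial visit with both surveys before the week-1 visit.

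**The concern.** This is delayed entry on an onset clock. Time is counted from the first symptom, but a patient is observed only from enrolment. Anyone whose smell returned in between is seen only if they still join a trial of a treatment for smell loss. If such people join less often than others, the enrolled group is weighted towards slow recovery, and its scores at a given week from onset look worse than those of all patients who lost their sense of smell.

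The protocol's own Background suggests that the missing group may be large: it cites a European study "with early recovery of olfactory function in just under half of patients". The Summary also aims the intervention at the subacute period, after the earliest phase.

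On the onset clock, week-1 and week-2 scores can come only from patients enrolled within one or two weeks of onset. The early and late parts of the course would then describe different subsets of patients. At stake is the guidance given to newly affected patients, which is the product of question 1.

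**Working it through.** **No figure to reproduce.** The protocol states no recovery proportion, entry delay or early-recovery share for its own cohort. The recruitment goal of 176 does not enter this point. All values below are assumptions chosen to show direction and range.

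**Inputs**
- R = true proportion recovered by six weeks from onset: 0.60, varied from 0.50 to 0.80.
- E = share recovered before they could enrol: 0.20 and 0.45. The second is an assumed reading of the Background's statement, which gives no time window.
- k = enrolment rate of early recoverers relative to everyone else: 0, 0.5 and 1.

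**Formula.** Among those enrolled, the proportion recovered by week 6 is

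observed = [(R − E) + kE] / [(1 − E) + kE].

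With k = 0 this is (R − E)/(1 − E). With k = 1 it equals R.

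**Results for R = 0.60**

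| E | k | Calculation | Observed | Shortfall |
|---|---|---|---|---|
| 0.20 | 0 | 0.40/0.80 | 50% | 10 points |
| 0.20 | 0.5 | 0.50/0.90 | 56% | 4 points |
| 0.45 | 0 | 0.15/0.55 | 27% | 33 points |
| 0.45 | 0.5 | 0.375/0.775 | 48% | 12 points |
| either | 1 | R | 60% | 0 |

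**Sensitivity to R (k = 0).** At E = 0.20, a true 50% appears as 0.30/0.80 = 38% and a true 80% as 0.60/0.80 = 75%. At E = 0.45 they appear as 0.05/0.55 = 9% and 0.35/0.55 = 64%.

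**Sensitivity to the entry delay.** Assume a constant recovery rate with R = 0.60 and that only patients still affected enrol, at week L. Then observed = 1 − 0.40^((6 − L)/6), which gives 53%, 46%, 37% and 26% for L = 1, 2, 3 and 4.

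The direction is the same whenever E > 0 and k < 1. The size depends on E, k and the delay, none of which the protocol gives.

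**The clock.** On the onset reading (endpoint and procedures sections), the week-1 score exists only for patients enrolled within a week of onset. On the enrolment reading (initial visit, then one, two, four and six weeks), every retained patient can supply all the scores. The protocol supports both readings. The enrolment reading cures the uneven subsets but does not bring back people who recovered before contact.

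**The case against.** Several parts of the opposing case stand.

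- **Persistence is not an entry rule.** A reader might infer that patients must still be affected to enrol. Neither the inclusion nor the exclusion criterion says so; the present-tense wording on identification and the treatment purpose only suggest it. Under-enrolment of recovered people is therefore likely but not certain.
- **Recruitment is not only by care-seeking.** The data-warehouse list is defined by COVID status, the team makes the contact, and application users had agreed to be contacted. These routes soften the selection. They do not remove the delay or the reduced motive of a recovered person to take a supplement for six weeks.
- **No recovery event is defined.** The outcomes are scores, and BSIT is taken once. The percentages above illustrate any recovery proportion or average score used for prognosis; they are not an output the protocol promises.
- **The onset clock is not uniform.** The statement about week-1 and week-2 scores holds only on the onset reading.
- **An SAP may handle delayed entry.** It could define the risk set, but it cannot recover contacts who were never counted at screening, and the data listed in the protocol include no such count.

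A reader might also infer that the treatment effect is biased. It is not biased by this mechanism, because the selection happens before randomisation and applies to both arms alike.

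**Conclusion.** The point holds in a limited form. Question 1 is tied to an onset clock, entry is later and without a time limit, and nothing listed shows who had already recovered. A prognosis stated from onset would be too pessimistic to the extent that early recoverers under-enrol.

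The size cannot be fixed from the protocol. With a true 60% recovery, the illustrated shortfall is 4 to 12 points if early recoverers enrol at half the rate of others, and 10 to 33 points if none enrol, for early-recovery shares of 20% and 45%. A reader might take the largest figure as the expected bias. The documents do not support that: it needs all of the early recovery cited in the Background to precede enrolment and none of those patients to join.

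The harm is confined to the descriptive aim. The change is worth making because it is cheap and alters what question 1 can conclude.

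**What to change.** 1. State one time origin for the week-1, 2, 4 and 6 assessments, and reconcile the endpoint and procedures sections with the two data-collection sections.
2. At enrolment, record whether smell loss is still present and the number of days since onset. Symptom onset is already part of the history taken at the initial visit.
3. In the screening log, count contacts whose smell loss had already resolved, so that the early-recovery share among contacts is known.
4. Report the natural-history scores in the placebo arm by time since enrolment. Use time since onset with delayed entry only if a dated recovery event is defined; a single BSIT does not provide one.
5. Word the prognosis as applying to patients still affected at entry, and give the distribution of days since onset beside it.

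The cost is one extra screening item, an explicit smell-status entry at enrolment, and some protocol wording. The downside is a narrower prognosis claim. The randomised comparison needs no change on this account.

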### **Settings and Resources**

#### Specify Other Setting of Human Research

This study will be executed at the Icahn School of Medicine at Mount Sinai. Patients will be recruited from the practices of faculty in the Department of Otolaryngology – Head and Neck Surgery and via the STOP COVID NYC web-based application (IRB 20-03271). All research will be conducted at the Icahn School of Medicine at Mount Sinai. No research will be conducted outside of the Icahn School of Medicine at Mount Sinai.

#### Feasibility of Meeting Recruitment Goals

Given the current 2020 COVID-19 pandemic and the high prevalence of this condition in the New York City area, combined with the high incidence of anosmia with COVID-19 infection, we anticipate relative ease in meeting recruitment goals.

#### Facilities To Be Used for Conducting Research

A portion of the patients will be recruited at Otolaryngology Faculty Practice Associates via telemedicine or through the STOP COVID NYC web-based application.

#### Involvement of the Community in the Design and Conduct of Research

There is no anticipated involvement of the community in the design and conduct of this research project.

### **Subjects**

#### Inclusion Criteria

Adults ( $\geq 18$  years of age) with self-reported new-onset olfactory dysfunction and a positive COVID-19 diagnosis will be deemed eligible for inclusion.

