### Specify Other Recruitment Method

Patients will be recruited (utilizing inclusion and exclusion criteria outlined above) through the Otolaryngology Faculty Practices and the Mount Sinai Data Warehouse list of COVID-19 positive patients diagnosed at Mount Sinai Hospital as well as the web based application *STOP COVID NYC* (IRB 20-03271).

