### How Participants Will Be Identified

Participants who are > 18 years of age, have self-reported anosmia and a positive COVID-19 diagnosis will be identified through the Mount Sinai Otolaryngology Faculty Practices and through the web-based application *STOP COVID NYC* (IRB 20-03271).

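### No maximum time from smell-loss onset to randomisation is set, although the aim is the subacute period and the primary test is fixed at 6 weeks from onset

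*Protocol*

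**What the plan says.** The Research Questions part of the Summary gives the therapeutic aim as "evaluating whether there is a therapeutic role for omega-3 supplementation during the subacute period". The protocol does not express subacute in days or weeks. The Background describes assessing olfactory function over the 6 weeks that follow infection.

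The Inclusion Criteria admit adults "with self-reported new-onset olfactory dysfunction and a positive COVID-19 diagnosis will be deemed eligible for inclusion". The Exclusion Criteria touch on timing only indirectly. They remove "Patients with pre-existing self-reported olfactory dysfunction" and "Patients without a positive COVID-19 PCR result obtained through nasopharyngeal swab", with no limit on the age of the PCR result.

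How Participants Will Be Identified refers to people who "have self-reported anosmia and a positive COVID-19 diagnosis will be identified through the Mount Sinai Otolaryngology Faculty Practices" or through a web application, with no time window. Specify Other Recruitment Method adds "the Mount Sinai Data Warehouse list of COVID-19 positive patients diagnosed at Mount Sinai Hospital", with no date range. How Participants Will Be Screened refers back to the same criteria.

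Primary and Secondary Study Endpoints has the BSIT "administered 6 weeks from symptom onset" and the two surveys "administered at time points of 1, 2, 4, and 6 weeks after symptom onset". Description of Procedures Being Performed repeats both timings and gives 6 weeks of treatment after randomisation.

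**The concern.** A screener applying the criteria literally has no cut-off for duration of smell loss. Beside the exclusion of earlier smell loss, new-onset can be read simply as new with COVID-19, so it is not an enforceable time limit. The criteria can therefore admit patients who are outside the period the trial says it studies, including some whose primary test date precedes their randomisation.

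Three things are at stake:

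- whether the primary endpoint can be obtained, as defined, in every eligible patient;
- how much treatment precedes it;
- whether the randomised population matches the subacute question.

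The initial-visit list under Description of Health Information that Will Be Viewed, Recorded, Or Generated contains the two surveys but no BSIT. No baseline score on the primary measure is therefore available to absorb differences related to symptom duration.

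**Working it through.** **Step 1: look for a limit.** Each section that could hold one was read.

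| Section | Timing content | Upper limit on duration? |
|---|---|---|
| Inclusion Criteria | new-onset, undefined | No |
| Exclusion Criteria | no earlier smell loss; positive PCR | No |
| Specify Other Recruitment Method | list of diagnosed patients | No |
| How Participants Will Be Identified | anosmia and positive diagnosis | No |
| How Participants Will Be Screened | refers to the criteria | No |

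Onset and duration of symptoms are recorded at the initial visit, but not used for eligibility.

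**Step 2: follow the from-onset schedule.** Let t be the weeks from onset to randomisation. The inputs are a BSIT at week 6 from onset and surveys at weeks 1, 2, 4 and 6 from onset (Primary and Secondary Study Endpoints), with treatment starting after randomisation (Description of Procedures Being Performed).

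Maximum treatment before the BSIT = max(0, 6 - t) weeks. A survey date has passed if its week number is less than t.

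| t (weeks) | Maximum treatment before BSIT (weeks) | Survey dates already past | Survey dates left |
|---|---|---|---|
| 0 | 6 | none | 4 |
| 1 | 5 | none | 4 |
| 2 | 4 | 1 | 3 |
| 3 | 3 | 1, 2 | 2 |
| 4 | 2 | 1, 2 | 2 |
| 5 | 1 | 1, 2, 4 | 1 |
| 6 | 0 | 1, 2, 4 | 1 (same day) |
| over 6 | 0; test date precedes randomisation | 1, 2, 4, 6 | 0 |

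These are upper bounds, because the supplement or placebo is sent to the home address after enrolment. Only t = 0 allows the full 6 weeks before the test. The last column excludes the surveys taken at the initial visit, which every enrolled patient has.

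**Step 3: follow the other reading of the schedule.** Description of Data that Will Be Collected Included Long-term Follow-Up and the visit lists in the Data section describe an initial visit, then follow-up at 1, 2, 4 and 6 weeks, without naming onset as the origin. If those weeks run from randomisation, every patient can complete 6 weeks of treatment before the BSIT and no test date has passed. The time from onset to the BSIT is then t + 6 weeks: 7 weeks for t = 1, 10 weeks for t = 4, and longer without limit. The spread in t passes directly into the spread in time since onset at the test.

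**Step 4: what cannot be computed.** The protocol gives no distribution of t, no BSIT standard deviation and no assumed effect. The number of late enrollees and the loss of power therefore cannot be derived from it, and the conclusion does not depend on either.

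**The case against.** The strongest reply is that the passed-date harm depends wholly on timing visits from onset, which the follow-up and data-collection sections do not repeat. That is correct. On a from-randomisation reading, only the mixture of symptom durations remains.

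The second reply is that the protocol clearly intends early enrolment: it speaks of new-onset loss, a subacute period and a week-1 survey. That also stands as evidence of intent. But none of these is an eligibility rule, and eligibility belongs in the protocol rather than in an analysis plan.

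Several stronger readings are tempting, and the protocol does not support them:

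- **Bias between arms.** Allocation is randomised 1:1, so mixed durations are balanced in expectation. The harm is to the definition of the endpoint, to precision and to the target population. An unseen analysis plan may adjust for duration, since onset is recorded.
- **A large share of patients lost.** No figure in the protocol supports any particular proportion. Nor does it say that the Data Warehouse list is cumulative or covers everyone diagnosed, and several sections name only the practices and the web application as sources.
- **Loss of many months or years being likely.** It is allowed as written, but nothing shows that it would be common. It is also bounded by the exclusion of pre-existing loss and by the start of the pandemic.
- **A natural-history curve without an origin.** Surveys timed from onset share one. Late enrolment leaves early points missing.
- **A measured fall in recovery with duration.** The two recovery figures in the Background come from different populations (COVID-19, and post-infectious loss generally). They do not quantify an effect of duration in COVID-19.

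**Conclusion.** The point holds as a gap between eligibility, aim and endpoint, and should be fixed. On the schedule in the endpoint section, treatment before the primary test is capped at 6 - t weeks, and an eligible patient beyond 6 weeks from onset has no primary endpoint as defined. This part rests on the from-onset timing being meant literally.

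If visits run from randomisation, what remains is milder: a population wider than the subacute question, and extra variance in a single BSIT score with no scheduled baseline. The protocol does not allow that variance to be quantified. Under neither reading is the comparison of arms systematically biased by the missing limit.

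**What to change.** Add to the Inclusion Criteria a maximum interval from smell-loss onset to randomisation. The sponsor should choose the number, and it should serve as the protocol's definition of subacute.

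The choice is tied to the visit origin:

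- **If the from-onset schedule is kept,** the limit T must be well under 6 weeks, because it guarantees at most 6 - T weeks of treatment before the BSIT. Early surveys will then be missing for later enrollees. Keeping all four survey dates ahead of every patient would require randomisation within 1 week of onset, after PCR, screening and consent, which may not be practical.
- **If a longer limit is wanted,** time the visits from randomisation, and bring Primary and Secondary Study Endpoints and Description of Procedures Being Performed into line with the follow-up and data-collection sections.

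Check the onset date at screening; it is already collected at the initial visit. For the Data Warehouse list, pre-filter on diagnosis date, since the protocol does not show that the list holds onset dates, and confirm onset with the patient.

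The cost is an amendment of one criterion, a filter on one recruitment source and a smaller eligible pool. Feasibility of Meeting Recruitment Goals expects recruitment to be relatively easy, which suggests that the loss is tolerable.
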